Evaluation will be performed before (pre-intervention testing), after (post-intervention testing), and 2 weeks after the therapy (follow up testing). Clinical sensorimotor function of the hand will be assessed using clinical tests, such as the Nine Hole Peg, Action Research Arm, Box and Block test to assess dexterity, as well as the Semmes-Weinstein and Grating Orientation tests to assess sensation. Secondarily, the Stroke Impact Scale and Stroke-Specific Quality of Life Scale will be recorded to assess the potential for the light vibration stimulation to impact patients' self-care abilities. Neurophysiologic evaluation will be performed using the MRI including an anatomical scan, diffusional kurtosis imaging (DKI), and functional MRI (fMRI) during grip, TMS including resting and active motor thresholds and motor evoked potential peak-to-peak amplitudes (all of these variables are routinely used in MUSC TMS evaluation protocols), and EEG evoked potentials and frequency power modulation during grip.

Each subject will visit MUSC for a total of 9 to 12 times over a period of a month. The pre-intervention testing will include screening, clinical hand function assessment, MRI, TMS and EEG. There will be six therapy visits lasting 2 hours each. Post-treatment evaluation will include clinical hand function assessment, MRI, TMS, and EEG after the completion of therapy. Follow up testing will include clinical hand function, TMS, and EEG again 2 weeks after the completion of therapy. Each set of evaluations (pre, post, and follow up testing) can be performed over 2 days to minimize participant fatigue.

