Subjects will be paid \$100 total per set of evaluations. For pre- and post-testing, the participant will receive \$25 for each type of evaluation completed (i.e., clinical hand function, MRI, TMS, and EEG) for a total of \$100. For follow-up evaluations, the participant will receive \$33 for clinical hand function, \$33 for TMS, and \$34 EEG for a total of \$100. The participant will receive \$25 per therapy visit for participation in this study. There will be a total of 11 evaluations sessions and 6 therapy visits. If they complete all evaluations and therapy visits, they will receive a total of \$450. If they stop participating in the study, they can keep the payment they have already received, but will not receive any more compensation. If the subject does not complete one of the assessments due to scheduling conflicts or safety risks (see Section 2.b.), the subject will not receive remuneration for that portion of the study. The payment will be in cash, at the end of each visit.

Analysis: Repeated measures ANOVA with post hoc comparisons will be used to determine if each clinical hand function score improves more for the experimental compared with the control group. A significant interaction between time (pre, post, 2 weeks after) and group (experimental/control) will support the hypothesis. Pearson's correlations between the mean change in clinical hand function scores and each of the neurophysiologic measures will be examined to identify relevant neurophysiologic measures for hand function.

Expected Outcomes: Greater recovery of dexterous hand function is expected with the light vibration stimulation (with a significant session×group interaction). This exciting finding will be the first to demonstrate that this unperceivable vibration stimulation at the wrist improves hand therapy outcomes.

E. PROTECTION OF HUMAN SUBJECTS

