9. After completing all evaluations, both groups will receive upper limb therapy 3 times a week for 2 consecutive weeks (for a total of 6 sessions) while wearing a vibrator at the wrist. An off-the-shelf mechanical vibrator in the size of a dime will be used. During therapy, Group A will receive vibration at the wrist at the level that is imperceptible. Group B will receive placebo, also in zero vibration at the wrist, during therapy. Both groups will not feel any vibration at the wrist during therapy, because the vibration is either very small or none. The therapy will focus on object manipulation, dexterous hand movement, and coordinated hand and arm movements.
10. After the last therapy session, all four evaluations (hand clinical function, MRI, TMS, and EEG) will be performed again.
11. Two weeks after the last therapy session, the subject will come to MUSC again to go through the three evaluations again (hand clinical function, TMS, and EEG).

Thirty chronic stroke survivors will be recruited (with 15 in each of the control and experimental groups). The age range will be 21 and older.

The inclusion criteria are mild to moderate impairment in upper extremity function (approximately 30 to 60 on the Fugl-Meyer Upper Extremity without the reflex portion). Exclusion criteria are cognitive dysfunction as evidenced by inability to follow three-step instructions and/or provide consent to participate in the study, stroke<3 months (to avoid interference with acute care), treatment with botox in the affected arm within 3 months of start of study, and age <21. Individuals with MRI contraindications (e.g., metal in the body, claustrophobia, pregnancy) or TMS contraindications (e.g., history of seizure, concussion, pregnancy) may still be considered for the study, but will not complete the contraindicated evaluation. Inclusion is based on clinical assessment, because recovery relates most with initial impairment level, not lesion characteristics.

Targeted/Planned Enrollment Table

Total Planned Enrollment: 30

TARGETED/PLANNED ENROLLMENT: Number of Subjects

Ethnic Category	Sex/Gender		
	Females	Males	Total
Hispanic or Latino	2	2	4
Not Hispanic or Latino	13	13	26
Ethnic Category: Total of All Subjects*	30		
Racial Categories			
American Indian/Alaska Native	0	0	0
Asian	1	1	2
Native Hawaiian or Other Pacific Islander	0	0	0
Black or African American	4	4	8
White	10	10	20
Racial Categories: Total of All Subjects*	15	15	30

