1. Loss of confidentiality: Appropriate steps will be taken to protect any information collected. The data from test results will be de-identified once it has been collected and before it is stored. This means individual results would not be able to be linked to the subject by others who review the results of this research. The linkage between subject codes and identities as well as all other identifiable information including consent/HIPPA forms will be stored in a locked room and be accessible only to the study personnel.

2. TMS: The MUSC Brain Stim Laboratory requires that all subjects receiving TMS and MRI complete a screening questionnaire to ensure that the person does not have any loose metal objects like earrings or nose rings or a piece of metal in the body such as a fragment in the eye, aneurysm clips, ear implants, spinal nerve stimulators, a pacemaker, or an implant electrical device. A person must be screened before each TMS and/or MRI exam. Persons who do not meet the screening criteria for TMS or MRI may still be considered eligible for the study, but will not complete these evaluations.

The primary safety concern with TMS is the induction of seizures; however, the incidence of seizures is very low and mostly associated with high frequency repetitive TMS (rTMS) which will not be used in this project. Instead we will use single-pulse TMS, which is much safer and we will follow published "gold standard" safety guidelines for diagnostic TMS to minimize the risk of inducing a seizure (*Groppa et al. 2012*).

Hearing protection for all subjects during TMS will be provided. Stimulation sessions will be stopped immediately with any complaints of discomfort or for any complaints of dizziness or light-headedness. There are no lower-risk methods available to gain the same scientific information.

A TMS stimulus may feel like a slight tap on the skull. There is a very low risk of scalp discomfort. The subject will be asked to notify the experimenter if s/he experiences these. The headache or changes in cognitive function is expressed, the subject will stop participating in the study.

Persons with potential for pregnancy will not have the TMS stimulation. Persons with a history of seizures will not have the TMS stimulation.

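### The plan does not say how subjects with a missed visit enter the three-visit repeated measures ANOVA; a mixed model on all observed hand-function scores would be better and costs little

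*Combined protocol and SAP*

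**What the plan says.** The Analysis paragraph of section D states: "Repeated measures ANOVA with post hoc comparisons will be used to determine if each clinical hand function score improves more" for the experimental than for the control group. The deciding criterion follows: "A significant interaction between time (pre, post, 2 weeks after) and group (experimental/control) will support the hypothesis". Section E.1.a gives the size: "Thirty chronic stroke survivors will be recruited (with 15 in each of the control and experimental groups".

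Follow-up is a separate return visit. Section D says "Follow up testing will include clinical hand function, TMS, and EEG again 2 weeks after the completion of therapy", and section E.1.a, item 11, says "Two weeks after the last therapy session, the subject will come to MUSC again".

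Incomplete data are foreseen in three ways.

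- **Withdrawal.** The payment paragraph of section D says "If they stop participating in the study, they can keep the payment they have already received, but will not receive any more compensation". Section E.2.b adds a safety route by which a subject leaves the study after certain symptoms around TMS.
- **Missed assessments.** The payment paragraph also covers the case "If the subject does not complete one of the assessments due to scheduling conflicts or safety risks (see Section 2.b" and states only that the missed part is not paid.
- **MRI or TMS skipped after screening.** Such subjects "may still be considered eligible for the study, but will not complete these evaluations" (section E.2.b).

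No section names an analysis set, says that subjects are analysed as randomised, or gives a rule for a missing hand-function score.

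**The concern.** The interaction test uses three scores per subject. Conventional repeated measures ANOVA needs all three, so a subject who completes therapy and post-testing but misses the return visit contributes nothing to the test that decides the hypothesis, although two of the three scores were observed.

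With 15 per arm this costs power even when the loss is random. If missing follow-up is related to how well the subject responded, the false-positive rate also moves away from its nominal level. Because the plan is silent, the handling of incomplete subjects could be chosen after the data are seen.

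The third kind of missing data above is a separate matter. A skipped MRI or TMS evaluation leaves the hand-function scores intact and reaches only the Pearson correlations. Missed clinical visits and withdrawal are what reach the ANOVA.

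**Working it through.** **Inputs from the protocol:** 15 per arm, three visits, group-by-time interaction. **Not in the protocol, so assumed:** two-sided alpha 0.05, 80% power, equal correlation 0.7 between visits, and k = 1, 2 or 3 of 15 per arm missing only follow-up. The sample of 30 comes with no power inputs, so there is no stated figure to reproduce. Effects D are in SDs of change.

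**1. Scores lost.** Of 90 possible scores, 90 − 2k are observed. Completers supply 3 × (30 − 2k) = 90 − 6k. The difference, 4k = 4, 8 or 12 scores, is observed but unused.

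**2. Two-group comparison of change.** Two-sample t-test with n = 15 − k per arm, noncentrality D / √(2/n), 2n − 2 df. For n = 15, 1.06 / √(2/15) = 2.90; for n = 12, 1.06 / √(2/12) = 2.60.

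| n per arm | Detectable D at 80% power | Power at D = 1.06 |
|---|---|---|
| 15 | 1.060 | 80.0% |
| 14 | 1.100 | 77.0% |
| 13 | 1.145 | 73.7% |
| 12 | 1.197 | 69.9% |

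**3. The plan's own interaction test.** Assume a true benefit D at both post and follow-up, so the group difference is (0, D, D).

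- *Completers ANOVA.* With equal variances and correlations the noncentrality is λ = n × (2/3) × D², with 2 and 4(n − 1) df; the correlation cancels because D is in SDs of change. At D = 1.06, λ = 0.749n.
- *Mixed model on all observed scores.* V = 2[nΣ⁻¹ + kΣ₂⁻¹]⁻¹, where Σ is the three-visit covariance and Σ₂⁻¹ is the inverse of its pre-post block padded with zeros. λ = bᵀ(LVLᵀ)⁻¹b, where L takes post minus pre and follow-up minus pre, and both entries of b equal D√(2(1 − 0.7)). Denominator df = (90 − 2k) − 30 − 4. This treats the covariance as known.

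| Lost per arm | ANOVA λ (df) | ANOVA power | Mixed λ (df) | Mixed power |
|---|---|---|---|---|
| 0 | 11.24 (56) | 84.0% | 11.24 (56) | 84.0% |
| 1 | 10.49 (52) | 81.1% | 11.06 (54) | 83.3% |
| 2 | 9.74 (48) | 77.8% | 10.88 (52) | 82.6% |
| 3 | 8.99 (44) | 73.9% | 10.70 (50) | 81.8% |

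At D = 0.8 with three lost per arm, the same formulas give 48.5% (ANOVA) and 56.4% (mixed), against 58.9% with no loss. Simulation with a REML random-intercept fit agrees at D = 1.06: 84.4% with no loss, and 73.2% against 82.4% with three lost per arm. Simulated ANOVA power was 76 to 78% for two lost and 73 to 76% for three.

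**4. Informative loss, no true effect (simulated, correlation 0.7).**

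- Poorest pre-post changer lost in each arm: ANOVA false positives about 6%.
- Three poorest lost in each arm: 7 to 8%, mixed model 4.9%. The mean difference is not biased.
- Random loss of three per arm: 5.4% for both methods.
- Adverse case, three poorest lost in one arm only: from expected normal order statistics for n = 15, the spurious post benefit among completers is (1.736 + 1.248 + 0.948) / 12 = 0.328 SD. ANOVA false positives are 12%; the mixed model shows no bias and 5.3%.

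**5. Where the mixed model is not a cure (simulated, three lost).**

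- Loss depends on the unobserved follow-up change: both arms 6.4% against 7.3% for ANOVA; one arm 9.4% against 11.5%, with a spurious follow-up benefit of 0.24 against 0.33 SD.
- True correlations decay (0.8, then 0.64) but a random intercept is fitted: both arms 6.5% against 8.1%; one arm 7.3% against 11.7%, with follow-up bias of 0.095 against 0.217 SD.
- A subject who leaves before post-testing has only a pre score, so neither method gains.

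**The case against.** **The plan does not say that incomplete subjects are dropped.** Correct. That is how the method conventionally behaves. The documented fault is an omission; with complete data and a matching covariance the two methods give essentially the same test.

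**The post scores need not be lost.** Section D plans post hoc comparisons and speaks of comparing post-therapy changes. A pre-post comparison on everyone with both scores keeps 15 per arm when only follow-up is missed, with about 80% power at 1.06 SD. This stands, and it limits the claim to the interaction test. That test, however, is the one the plan names as support for its hypothesis.

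**Loss may be light.** The study runs about a month, and the follow-up clinical test pays $33 against $25 at post-testing. No passage supports 20% loss. With one lost per arm, power falls only from 84% to 81%, which is why the range of one to three is shown.

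**A reader might infer that the comparison will be biased in favour of vibration.** The documents do not support this. It needs loss that is both related to response and uneven between arms. Stimulation is imperceptible, the therapist is blinded and follow-up is paid, so no passage gives a reason to expect uneven loss. The 0.33 SD and 12% figures are an adverse case only.

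**It is a 30-subject pilot.** True, but section D still rests its conclusion on a significant interaction, and each lost subject weighs more at this size.

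**Conclusion.** The concern holds as an omission with a cheap improvement available. The protocol foresees incomplete subjects and does not say how they enter its deciding test. If the ANOVA is run on completers, one to three subjects per arm missing only follow-up at random cost about 3 to 10 percentage points of interaction power at 1.06 SD, against about 1 to 2 points for the mixed model. False positives rise to about 6 to 8% if the poorest responders are lost in both arms.

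These sizes rest on an assumed loss rate, effect, alpha and visit correlation, none of which the protocol gives. The documents do not show that observed scores will be discarded, that loss will reach 20%, or that it will differ between arms.

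**What to change.** 1. Replace the repeated measures ANOVA with a linear mixed model with time, group and time-by-group, using every observed hand-function score of all randomised subjects, analysed as randomised. Fix the covariance in advance, for example REML with a random intercept or an unstructured covariance, with Kenward-Roger degrees of freedom. Unstructured avoids the mismatch in step 5 of the working; the power figures above are for equal correlations and were not computed for that choice.
2. State which scores of a subject who stops participating enter the analysis.
3. Add one sensitivity analysis that shifts the missing follow-up scores over a stated range and reports whether the conclusion changes.

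The cost is protocol wording and slightly more analysis work, with no extra visits, assessments, subjects or payments. The downside is reliance on missing at random: the model reduces but does not remove bias if loss depends on unobserved scores or the covariance is mis-specified.

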**Medical University of South Carolina
Protocol**

PI Name: [name]

Study Title: Sensory Stimulation to Enhance Hand Function Post Stroke

NCT02675764

TABLE OF CONTENTS

A. SPECIFIC AIMS	2
B. BACKGROUND AND SIGNIFICANCE	2
C. PRELIMINARY STUDIES	2
D. RESEARCH DESIGN AND METHODS	2
E. PROTECTION OF HUMAN SUBJECTS	3
F. REFERENCES/LITERATURE CITATIONS	7
G. FACILITES AVAILABLE	8

A. SPECIFIC AIMS

The objective of this pilot project is to assess the impact of the novel sensory vibration stimulation technique we have developed in enhancing outcomes of hand therapy as well as the central nervous system responsiveness in chronic stroke survivors. This impact will be assessed in a double-blind stratified randomized controlled trial for stroke survivors. The hypothesis is that improvement in hand function will be greater for the experimental group receiving the wrist subthreshold vibrotactile stimulation during therapy compared with the control group who will wear the device with no vibration (placebo), and that this better improvement in hand function is associated with neurophysiologic measures of central nervous system responsiveness.

B. BACKGROUND AND SIGNIFICANCE

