D. RESEARCH DESIGN AND METHODS

The hypotheses will be tested in a double-blind stratified randomized controlled trial. Experimental and control groups will be compared for post-therapy changes in hand function. To obtain two comparable groups, stroke subjects will be stratified by their initial hand motor and sensory scores (Fugl-Meyer and Semmes-Weinstein mild vs. moderate). Subjects will be randomly and blindly assigned to either the experimental or the control group. A standardized task-practice therapy focused on dexterous object manipulation and multi-joint upper extremity coordination will be used, since the intervention targets sensory feedback-based motor control. The research therapists at the SC Stroke Recovery Research Center have been trained in its implementation and routinely use this protocol. Each subject will receive therapy two hours/day, 3 days/week for 2 weeks. The duration of 2 weeks is deemed sufficient to result in statistically greater improvement in motor outcome and cortical reorganization (seen using fMRI/TMS) for the experimental compared to the control group. The two groups will receive therapy of equal intensity individually in the same room supervised by the same therapist who is blinded to the group and does not know how the coin-sized device providing the light vibration works. Tactor (EAI, Casselberry, FL) generating light vibration in our preliminary studies will be applied to the wrist. At the beginning of each therapy session, the subject's sensory threshold will be determined and the vibrating intensity will be adjusted to either 60% of the sensory threshold or zero, depending on the group. Blinding to the light vibration stimulation is possible because subjects cannot perceive subthreshold (imperceptible) vibration, thus they do not know whether they are receiving the vibration or not.

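### Vibration's effect on the central nervous system is part of the trial's objective, but no MRI, TMS or EEG measure is compared between the groups

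*Combined protocol and SAP*

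**What the plan says.** Section A (Specific Aims) gives the objective as the impact of the technique in "enhancing outcomes of hand therapy as well as the central nervous system responsiveness in chronic stroke survivors", and continues: "This impact will be assessed in a double-blind stratified randomized controlled trial for stroke survivors". The hypothesis sentence that follows is narrower on the neurophysiologic side. It says that "this better improvement in hand function is associated with neurophysiologic measures of central nervous system responsiveness".

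In Section D (Research Design and Methods), the design paragraph names one group comparison: "Experimental and control groups will be compared for post-therapy changes in hand function". The same paragraph justifies two weeks of therapy as enough to produce "statistically greater improvement in motor outcome and cortical reorganization (seen using fMRI/TMS) for the experimental compared to the control group".

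The evaluation paragraph of Section D lists MRI (anatomical scan, DKI, fMRI), "TMS including resting and active motor thresholds and motor evoked potential peak-to-peak amplitudes", and "EEG evoked potentials and frequency power modulation during grip". All three types of evaluation are done before and after therapy; TMS and EEG are repeated at the two-week follow-up, MRI is not.

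The Analysis paragraph of Section D gives a repeated measures ANOVA, judged on the time-by-group interaction, for each clinical hand function score. For the neurophysiologic data it gives Pearson "correlations between the mean change in clinical hand function scores and each of the neurophysiologic measures will be examined", with the stated purpose of finding which measures are relevant to hand function.

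**The concern.** Whether vibration changes CNS responsiveness is a treatment-effect question, and randomisation is what allows it to be answered. The plan asks that question in the objective and anticipates the answer in the rationale for treatment duration, but has no analysis that could give it. The correlation asks something else: whether people whose hand function changed more also differ on a neurophysiologic measure. A measure can track hand function without responding to vibration, and can respond to vibration without tracking hand function.

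Followed as written, the trial would collect up to 8 MRI, TMS and EEG evaluations per person (3 before therapy, 3 after, 2 at follow-up) and leave the CNS part of its objective without a result.

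**Working it through.** The documents give no significance level, effect size, SD or power, so there is no figure to reproduce. The textual comparison comes first; the calculations only illustrate size.

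**What is asked and what is analysed**

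| Question | Where asked | Planned analysis |
|---|---|---|
| Does vibration improve hand function? | A, objective and hypothesis; D, design | Group-by-time ANOVA |
| Is improvement associated with neurophysiologic measures? | A, hypothesis | Pearson correlation |
| Does vibration change CNS responsiveness? | A, objective; D, expectation for fMRI/TMS | None in the documents |

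**Can the correlation stand in for the third row?** Inputs: 15 per group (Section E.1.a). Assumed: two-sided 5%, normal data, and the effect sizes below.

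- Group comparison: noncentral t with noncentrality d × √(15/2) and 28 df. ANCOVA divides the residual SD by using √(1 − r²) in place of 1, with 27 df and an assumed pre-post correlation r = 0.5.
- Correlation: 40,000 simulated trials per effect size, with the measure shifted, hand function not shifted, and no within-group association.

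| Shift in the measure | Correlation significant | Group t-test | ANCOVA |
|---|---|---|---|
| 0.5 SD | 5% | 26% | 33% |
| 0.8 SD | 5% | 56% | 68% |
| 1.06 SD | 5% | 80% | 90% |

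The converse also holds. With a true correlation of 0.6 and no group effect on the measure, the correlation was significant in 96% of 4,000 simulated trials and the group test in 5%. The two analyses answer different questions.

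**Precision of an added comparison.** The 95% CI half-width is t × √(2/n) SD, multiplied by √0.75 for ANCOVA at r = 0.5. Section E.1.a allows people with MRI or TMS contraindications to enrol and skip that evaluation, but gives no number, so smaller n are assumed as well.

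| n per group | Unadjusted | ANCOVA |
|---|---|---|
| 15 | 0.75 SD | 0.65 SD |
| 12 | 0.85 SD | 0.74 SD |
| 10 | 0.94 SD | 0.82 SD |

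**Multiplicity.** One summary each for DKI and fMRI, three for TMS and two for EEG make 7 comparisons after therapy. TMS and EEG make 5 at follow-up, so 12 in all. With no effect, the chance of at least one p < 0.05 is 1 − 0.95^12 = 46% if the tests are independent, and 32% if they correlate at 0.5. The count holds only with one summary per category: 20 independent comparisons would give 64%, and 30 would give 79%.

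**Definition of the correlation (minor).** The sentence does not fix which neurophysiologic value is used or whether the groups are pooled. Suppose hand change correlates 0.60 with neurophysiologic change, and only through that change, with pre-post correlation 0.7 and equal SDs. The change then has SD √(2 × 0.3) = 0.775 and covariance 0.7 − 1 = −0.3 with baseline. The correlation with the baseline value is 0.60 × (−0.3)/0.775 = −0.23, and with the post value +0.23.

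If the groups are pooled, both changes are shifted by d SD and there is no within-group association, the true pooled correlation is (d²/4)/(1 + d²/4): 0.06, 0.14 and 0.20 at d = 0.5, 0.8 and 1.0. It is significant in 6%, 11% and 19% of simulated trials, against 5% after adjustment for group.

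**The case against.** The best defence is that the operational hypothesis is associational and is covered. Section D says the hypotheses will be tested, and the Analysis paragraph supplies an analysis for each part: ANOVA for hand function, correlation for association. The Expected Outcomes paragraph claims only hand function, and the cortical reorganisation phrase justifies duration and is not an endpoint statement. This stands as far as it goes: a reader might infer that the neurophysiologic hypothesis has no analysis at all, and that would be wrong. It does not remove the mismatch with the objective, which is worded as an impact to be assessed by randomised comparison.

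The 5% in the first table follows by construction from assuming a measure unrelated to function. That is fair: it shows that a correlation is not a group test and does not estimate a loss in this trial.

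A reader might also infer that the correlation is wholly undefined, with baseline and change equally likely. The documents do not support that. Section E.1.a (item 5) presents all four evaluations as measures of recovery, and MRI is repeated after therapy, which favours change. The sentence can also be read so that the change applies to both variables. What is missing is mostly detail.

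Nor should the pooled correlation be called invalid. The hypothesis concerns the experimental group's better improvement, so an association carried partly by the group difference is arguably part of what is hypothesised. The inflation rests on assumed shifts in both variables and is only 6% against 5% at 0.5 SD.

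**Conclusion.** The point holds. A stated part of the objective, and an explicit expectation of a group difference on fMRI/TMS, have no between-group analysis, and the planned correlation cannot supply one. This rests on the text alone. The power, interval and multiplicity figures rest on assumed effects, a two-sided 5% level and an assumed pre-post correlation of 0.5.

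It is worth correcting, but limited in weight. The trial is a 30-person pilot, so any added comparison would be for estimation, and a null result would be inconclusive. Preferring ANCOVA to the protocol's own group-by-time model is a gain in precision and corrects no error: at r = 0.5 the variance factor is 1 − r² = 0.75, against 2(1 − r) = 1.0 for a change score. The undefined correlation variable is a secondary clarification. The hand-function comparison is unaffected.

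**What to change.** In the Analysis paragraph of Section D:

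1. Add an exploratory between-group comparison of a short, pre-named list of neurophysiologic summaries. An example is one DKI and one fMRI summary, the TMS thresholds and motor evoked potential amplitude with the hemisphere stated, and EEG summaries with component or frequency band and electrode stated. The evaluation paragraph is not yet that specific for EEG or for the TMS hemisphere.
2. Compare pre to post for all measures, and also at follow-up for TMS and EEG. Use baseline-adjusted ANCOVA or the protocol's own group-by-time model, in participants who completed that evaluation at the time points compared.
3. Report the number per group, the difference and its 95% CI. Label the results exploratory and state the number of comparisons (about 12 only with one summary per category).
4. As a clarification, state that the correlation uses change against change and over which interval, list any baseline-predictor correlation separately, and give a group-adjusted value beside the pooled one as a supplement.

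The cost is a paragraph of text and about 12 small models on data already collected, with no new visits or tests. The downside is the wide intervals shown above.

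If no group comparison is wanted, reword the objective in Section A and the expectation in Section D so that the CNS part is associational only, and still make the clarification in item 4. That costs two sentences and gives up the question of whether vibration affects the CNS.
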